## 4.2.2.3 Medically-Attended Adverse Event

An event will be considered as an MAAE if "Yes" is checked for "Is the event an MAAE?" in the CRF.

MAAE will be analyzed during the following time periods:

- Within 28 days after a vaccination
- During the period from 29 days after the vaccination up to M6 post-vaccination as part of the SAE (Serious MAAE) and at any time during the study as part of SAEs that are related or fatal (serious related or fatal MAAE)

## 4.2.2.4 SAEs

An event will be considered as a serious event if "Yes" is checked for "Serious" in the CRF.

SAEs will be analyzed throughout the study using the following periods:

- Within 28 days after a vaccination
- During the period from 29 days after the injection until the last participant contact at M6
- During the study for related SAEs (ie, all related SAEs occurred during the study)

## 4.2.2.5 Adverse Events of Special Interest

An event will be considered as an AESI if "Yes' is checked for "Is the event an AESI?" in the CRF.

AESIs will be analyzed throughout the study using the following periods:

- Within 28 days after a vaccination
- During the period from 29 days after the injection until the last participant contact at M6

#### 4.2.2.6 Other Safety Endpoints

#### 4.2.2.7 Pregnancy

This information will not be included in the analysis but will be listed separately. No derivation or imputation will be done.

#### 4.2.2.8 Action Taken

This information will be summarized as collected, including missing observations. No derivation or imputation will be done.

#### 4.2.2.9 Seriousness

This information will be summarized as collected. No derivation or imputation will be done.

#### 4.2.2.10 Outcome

This information will be summarized as collected. No derivation or imputation will be done.

#### 4.2.2.11 Causal Relationship

This information will be summarized as collected in the field "Relationship to study vaccine". Missing causal relationship will be handled as described in Section 5.3.2.2 Relationship to study procedure is only presented in the listing.

#### 4.2.2.12 Adverse Events Leading to Study Discontinuation

This information will be summarized as collected. A flag is available in the clinical database for all AEs in order to identify AEs leading to discontinuation before the end of active phase.

In general, the items that are counted are:

- Disposition table: A participant who, on the "Completion at End of Study" form question "What was the participant's status?" has "Adverse Event" checked.
- Safety overview table: A participant who has either on the "Completion at End of Study" form, question" What was the participant's status?" has "Adverse Event" checked or lists a solicited AE that has "Caused Study Termination" checked that is at least Grade 1 or an unsolicited AE that has "Caused Study Discontinuation" checked that is at least Grade 1 or missing and is within the time period indicated.

System Organ Class (SOC)/Preferred Term (PT) table: A solicited AE that has "Caused Study Termination" checked that is at least Grade 1 or an unsolicited AE that has "Caused Study Discontinuation" checked that is at least Grade 1 or missing and is within the time period indicated.

## 4.2.3 Efficacy

Not applicable

## 4.2.4 Derived Other Variables

## 4.2.4.1 Age for Demographics

Considering the Sanofi convention of date of birth collection, the age of a participant at the date of informed consent signature/visit 1 will be entered in the electronical CRF.

## 4.2.4.2 Duration of the Study

The durations are computed in days as follows:

Latest date of all participants (termination date, last visit date, date of last contact) - earliest date of all participants (date of visit V01) + 1.

## 4.2.4.3 Participant Duration

The duration of a participant participation in the study is computed as follows:

Maximum (Visit dates, Termination date, Follow-up date, Last contact date) - V01 date + 1.

## 5 Statistical Methods and Determination of Sample Size

The statistical analyses will be performed under the responsibility of the Sponsor's Biostatistics platform using SAS® 9.4 Version software or later.

The results of the statistical analysis will be available in the final clinical study report (CSR).

For descriptive purposes, the following statistics will be presented:

Baseline characteristics and	Categorical data	Number of participants.
follow-up description		Percentage of participants.
	Continuous data	Mean, standard deviation (SD), quartiles, minimum, and maximum.
Clinical safety results	Categorical data	Solicited: Number and percentage (95% CIs) of participants.
		Unsolicited: Number and percentage (95% CIs) of participants, and number of events.
Immunogenicity results         Categorical data (seroprotection, seroconversion, cutoff)         Numi		Number and percentage (95% CIs) of participants.
	Continuous data	Log10: Mean and standard deviation.
	(titer / data†)	Anti-Log10 (work on Log10 distribution, and anti-Log10 applied): Geometric mean, 95% CI of the geometric mean, quartiles, minimum, and maximum.
		Graphical representation by Reverse Cumulative Distribution Curve (RCDC).

Table 5.1: Descriptive statistics produced

The CI for the single proportion will be calculated using the exact binomial method (Clopper-Pearson method, quoted by Newcombe (2), ie, using the inverse of the beta integral with SAS®.

For immunogenicity results, assuming that Log10 transformation of the titers / data follows a normal distribution, at first, the mean and the 95% CI will be calculated on Log10 (titers / data) using the usual calculation for normal distribution (using Student's t distribution with n-1 degree of freedom), then antilog transformations will be applied to the results of calculations, in order to provide geometric means (GMs) and their 95% CI.

GM is defined as follows:

$$GM = \left(\prod_{i=1}^{n} y_{i}\right)^{1/n} = 10^{n} \left(\frac{1}{n} \sum_{i=1}^{n} \log \omega(y_{i})\right)$$

where  $(y_1, y_2, ..., y_n)$  are the observed titers or other data where applicable for each participant. Rounding rules on descriptive statistics will follow the Sanofi Pasteur standard technical guideline ("Conventions for the Presentation of Descriptive Statistics").

## 5.1 Statistical Methods

## 5.1.1 Hypotheses and Statistical Methods for Primary Objective(s)

## 5.1.1.1 Hypotheses

Primary analyses will be performed on the Per-Protocol Analyses Set and on Full Analysis Set.

The objective is to demonstrate that the humoral response in terms of seroconversion of vYF (Group 1) is non-inferior to the humoral response of Stamaril (Group 2) 28 days after a single dose in YF-naïve participants.

The percentages of participants with seroconversion 28 days after vaccination will be used to compare responses between Group 1 and Group 2 with the following hypotheses:

- H0 (Null hypothesis):  $p(vYF) p(Stamaril) \le -\delta$
- H1 (Alternative hypothesis):  $p(vYF) p(Stamaril) > -\delta$

Where  $\delta$  the non-inferiority margin is set to 5%.

Where p(vYF) and p(Stamaril) are the proportion of participants with seroconversion. Seroconversion is defined as a 4-fold increase in NAb titers as compared to pre-vaccination value.

In the last version of the protocol (version 4.0 approved on  $1^{st}$  July 2021), the D29 visit is to be performed with a time window of +3 days; a blood sample BL0003 has to be taken at the D29 visit.

However, the timing for the Phase II non-inferiority VYF03 study has been complicated by COVID epidemic waves and vaccination campaigns; when non-COVID work was resuming at Investigational sites, these studies were competing against other studies. As a direct consequence, the enrolments were delayed and longer than expected. Considering that the planned sample size was likely to be not reached, the Applicant worked on a mitigation plan based on the number of

evaluable subjects (derived from the attrition rate used for the statistical hypotheses) consisting of extending the time window of the D29 post-vaccination visit (initially defined as D29 +3 days) with a proposal to extend up to D29 +6 days as the immune responses should not be impacted by this extension. The analyses with a revised time window for the D29 visit +6 days will be presented as the primary analysis of the non-inferiority of the antibody response in terms of seroconversion rates 28 days after vaccine administration of one dose of vYF (administered on D01) compared to the antibody response after one dose of the Stamaril (administered on D01) in EU YF-naïve participants. If the primary objective is reached, in secondary objective, the originally planned analysis of the non-inferiority of the antibody response on D29 with a time window of +3 days will be presented too on the EU YF-naïve participants only and completed with a descriptive analysis in terms of seroconversion, seroprotection, GMT and GMTR.

#### 5.1.1.2 Statistical Methods

The non-inferiority will be demonstrated if the lower limit of the 2-sided 95% confidence interval (CI) of the difference between the 2 percentages is > -5%.

The CI of the difference in percentages will be computed using the Wilson score method without continuity correction as quoted by Newcombe (3) for seroconversion rates.

#### 5.1.2 Hypotheses and Statistical Methods for Secondary Objective(s)

#### 5.1.2.1 Hypotheses

No hypotheses will be tested. Descriptive statistics will be presented.

## 5.1.2.2 Statistical Methods

#### Immunogenicity:

Analyses will be performed on the Full Analyses Set.

The immunogenicity parameters will be described per vaccine group. Immunogenicity analyses will be provided on participants by YF serostatus and by FV serostatus.

The following parameters will be analyzed:

- GMT for each vaccine group
- Seroconversion rates: number and percentage of participants in each vaccine group converted with neutralizing antibody titer 4-fold increased compared to D01 up to M6: D11 (subset only) compared to D01, D29 compared to D01, M6 compared to D01; and yearly from Y1 to Y5 compared with the latest planned timepoint: Y1 compared to M6, Y2 compared to Y1, Y3 compared to Y2, Y4 compared to Y3, Y5 compared to Y4
- Within-group GMTR for each vaccine group post-vaccination injection, compared to D01 (D11/D01 [subset only], D29/D01, M6/D01 and yearly ratios: Y1/M6, Y2/Y1, Y3/Y2, Y4/Y3, Y5/Y4

- Number and percentage of participants (seroprotection rates) in each vaccine group with antibody titer ≥ 10 (1/dil) at baseline (D01) and at D11 (subset only†), D29, M6, and yearly from Y1 to Y5
- Distribution of titers against YF at each time point and corresponding RCDC

The 95% CIs will be calculated using:

- The normal approximate method for GMTs and GMTRs
- The exact binomial distribution for percentages (Clopper-Pearson's method, quoted by Newcombe)

Assuming that log10 transformation of the titers/ratios follows a normal distribution, first, the mean and 95% CI will be calculated on log10 (titers/ratios) using the usual calculation for normal distribution, then antilog transformations will be applied to the results of calculations, to compute GMTs/GMTRs and their 95% CIs.

Complementary immunogenicity analysis based on the planned analysis on D29 with a time window of +3 days will be performed on a sub-population of the Per-Protocol Analysis Set:

- Non-inferiority analysis of the antibody response on D29
- GMT for each vaccine group
- Seroconversion rates: number and percentage of participants in each vaccine group converted with neutralizing antibody titer 4-fold increase compared to the previous time point, at D29 compared to D01
- Within-group GMTR for each vaccine group D29 post-vaccination injection, compared to D01
- Number and percentage of participants (seroprotection rates) in each vaccine group with antibody titer  $\geq 10$  (1/dil) at baseline (D01) and at D29

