### International Certificate of Vaccination or Prophylaxis for YF Vaccination

At the end of the first interim analysis and at the end of the study, the Investigators will be provided with individual listings detailing for each participant the vaccine group assignment and the neutralizing antibody titers at the successive time points. Participants are responsible for

contacting the study site to obtain this information about which study group they were assigned to and which vaccine they received.

VYF03

Those participants enrolled in the Stamaril group can be provided by the investigational site with the ICVP for YF vaccination; and those participants enrolled in a vYF group would be informed that they need to obtain a licensed YF vaccine prior to travel to endemic areas.

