# 6.5 Concomitant Therapy

At the time of enrollment, ongoing medications and other therapies (eg, blood products) should be recorded in the source document as well as new medications prescribed for new medical conditions / AEs during study participation.

Documentation in the CRF of ongoing concomitant medication(s) will be limited to specific categories of medication(s) of interest beginning on the day of first vaccination. This may include medications of interest that were started prior to the day of vaccination.

Reportable medications will be collected in the CRF from the day of each vaccination to the end of the solicited and unsolicited follow-up period, except for use of any investigational or non-registered product (drug, vaccine or medical device), or vaccination with commercial YF vaccine, which will be collected for the entire study period .

Reportable medications include medications that impact or may impact the consistency of the safety information collected after any vaccination and/or the immune response to vaccination. Three standard categories of reportable medications are defined:

- Category 1: medications impacting or that may have an impact on the evaluation of the safety (eg, antipyretics, analgesics, and non-steroidal anti-inflammatory drugs [NSAIDs], systemic steroids/corticosteroids)
- Category 2: medications impacting or that may have an impact on the immune response (eg, other vaccines, blood products, antibiotic classes that may interfere with bioassays used by the Global Clinical Immunology [GCI] department or other testing laboratories, systemic steroids/corticosteroids, immune-suppressors, immune-modulators with immunosuppressive properties, anti-proliferative drugs such as DNA synthesis inhibitors)
- Category 3: medications impacting or that may have an impact on both the safety and the immune response (eg, systemic steroids/corticosteroids)

Any investigational or non-registered product (drug, vaccine or medical device), other than the study vaccine during the period beginning 29 days before the dose of study vaccine or during the study period, as well as receipt of a commercial YF vaccine, will be recorded as Category 3.

Dosage and administration route, homeopathic medication, topical and inhaled steroids, as well as topical, ophthalmic, and ear treatments will not be recorded. Topical analgesics should not be

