## 5.2 Analysis Sets

The following populations are defined:

Population	Description	
Randomized	All participants with data in the CRF.	
Full analysis set (FAS)	Subset of randomized participants who received at least 1 dose of the study vaccine or control vaccine and had a valid post-vaccination blood sample result.	
	Participants will be analyzed according to the intervention to which they were randomized.	
Safety Analysis Set (SafAS)	Participants who have received at least 1 dose of the study vaccines. All participants will have their safety analyzed according to the vaccine they actually received.	
	Safety data recorded for a vaccine received out of the protocol design will be excluded from the analysis (and listed separately).	
Per-protocol analysis set (PPAS)	Subset of the FAS. Participants presenting with at least one of the following relevant protocol deviations will be excluded from the PPAS:	
	Participant is not YF-naïve	
	Participant is recruited in Asia	
	• Participant did not meet all protocol-specified inclusion criteria or met at least one of the protocol-specified exclusion criteria	
	• Participant received a vaccine other than the one that he / she was randomized to receive	
	• Preparation and / or administration of vaccine was not done as per- protocol	
	Non-availability of other critical measurements for the primary analysis:	
	• Baseline serology sample was not collected in the protocol-specified time window or the serology sample was not drawn	
	• Participant did not provide the post-dose serology sample on Day 29 Visit (D28 after vaccination) in the proper time window or the blood sample was not drawn	
	• Participant received any therapy / medication / vaccine which could inhibit the immune response until the time point considered for the analysis (Day 29, Visit 4).	
	• In addition to the reasons listed above, participants will also be excluded from the PPAS if their baseline or post-vaccination serology sample at D29 (Visit 4) did not produce a valid test result (ie, results for all antigens are missing or out-of-range).	

	· · · · · · · · · · · · · · · · · · ·

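### Y1–Y5 persistence summaries have no rule for titres drawn after a licensed YF vaccine, which only vYF recipients are told they need before endemic travel, so vYF persistence can be inflated

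*SAP*

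**What the plan says.** **Release of group assignment.** Protocol 2.3.2, in the part on the International Certificate of Vaccination or Prophylaxis, states: "At the end of the first interim analysis and at the end of the study, the Investigators will be provided with individual listings". The listings give each participant's group and titres. Participants learn their group only if they ask, being responsible for "contacting the study site to obtain this information about which study group they were assigned to".

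**Different consequences by arm.** For the control arm: "Those participants enrolled in the Stamaril group can be provided by the investigational site with the ICVP for YF vaccination". For the other arm: "those participants enrolled in a vYF group would be informed that they need to obtain a licensed YF vaccine prior to travel to endemic areas". Protocol Appendix 10.2 confirms that results are released after the first interim so that sites can issue certificates to the Stamaril group. Protocol section 2 describes that certificate as valid for life.

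**Recording.** Protocol 6.5 stops collecting most medications after the early follow-up. It makes an exception for investigational or unregistered products "or vaccination with commercial YF vaccine, which will be collected for the entire study period". A commercial YF vaccine is classed as Category 3, the class that can affect both safety and immune response.

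**Analysis.** For GMT, GMTR, seroconversion, seroprotection and titre distributions through Y5, SAP 5.1.2.2 says "Analyses will be performed on the Full Analyses Set". In SAP 5.2 the FAS requires one dose and one valid post-vaccination result. SAP 5.3.1 covers missing values, outliers and quantification limits only. Neither mentions a later YF vaccine, and SAP 5.7 lists no change on this point.

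**The concern.** Maintenance of antibody over five years is a stated purpose of the trial (Protocol 2.1 and 2.3.2). A titre drawn after a licensed YF vaccine no longer measures the response to the study dose. The prompt to take that vaccine falls on one arm, after unblinding and before most of the persistence samples. The exclusion for planned endemic travel (criterion E17) covers only the first 6 months, and Protocol 4.4 and 7.2 keep participants in follow-up for five years.

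The persistence results are descriptive, but they will be read arm against arm. What is at stake is whether a vYF curve that holds up over time reflects vYF or a mixture of vYF and a licensed vaccine.

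**Working it through.** **1. Does any existing rule catch these titres?**
- The FAS definition does not. It has no time limit and no censoring.
- The PPAS exclusion for vaccines does not. It applies to another analysis set, stops at D29 and concerns products that could inhibit the response. The clause allowing that list to be extended is also confined to the PPAS.
- SAP 5.3.1 does not.
- The SafAS rule on vaccines received outside the protocol design concerns safety data only.

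**2. Which visits are exposed?** The first interim uses data to M6 (SAP 5.4), and SAP 5.7 says enrolment was slow. Some Y1 samples may therefore precede release of the listings, so exposure is mainly from Y2. SAP 5.4 also allows D01–D29 to be analysed separately; if that counted as the first interim, release would come sooner.

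**3. The plan's own figures.** None concerns revaccination. The sample-size text gives 304 + 152 = 456 evaluable EU participants out of 570 (456/570 = 0.80). I use these only for scale. Planned power cannot be reproduced because its inputs are redacted, and it is not needed here.

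**4. Size under assumptions.** Let r be the share of vYF samples at a visit drawn after a licensed dose, F the fold rise still present in them, and p the true vYF seroprotection rate. Assume no Stamaril recipients are revaccinated, all those revaccinated are seroprotected, and revaccination is unrelated to prior titre. The ranges for r, F and p are mine; the documents give none.

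- GMT: the mean log titre rises by r × log F, so the GMT is multiplied by F^r.
- Seroprotection: observed rate = p + r(1 − p).

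| r | GMT factor, F=4 | F=8 | F=16 | Seroprotection, p=90% | p=98% |
|---|---|---|---|---|---|
| 0 | 1 | 1 | 1 | 90.0% | 98.0% |
| 2% | 1.028 | 1.042 | 1.057 | 90.2% | 98.04% |
| 5% | 1.072 | 1.110 | 1.149 | 90.5% | 98.1% |
| 10% | 1.149 | 1.231 | 1.320 | 91.0% | 98.2% |
| 20% | 1.320 | 1.516 | 1.741 | 92.0% | 98.4% |

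If uptake ran at 2% or 5% a year over four yearly intervals, the cumulative share would be 1 − 0.98⁴ = 7.8% or 1 − 0.95⁴ = 18.5%, inside this range.

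**5. Year-on-year parameters.** From Y1, seroconversion and GMTR compare each visit with the one before it. If a share r is first revaccinated in an interval and a fraction q of them rise at least 4-fold, about r × q of the arm counts as newly seroconverted in that interval (at most 2–5% for 2–5% yearly uptake). GMTR is multiplied by F^r in that interval. The next interval starts from the boosted value, so waning of the boost would then lower the vYF GMTR.

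**6. Scale against sampling error.** With 304 and 152 sampled and an assumed log10 SD of 0.4–0.6, the 95% CI factor on a between-arm GMT ratio is 10^(1.96 × SD × √(1/304 + 1/152)) = 1.20–1.31. At 10% uptake the bias factor (1.15–1.32) is of the same order. For seroprotection at 90% in both arms, the half-width of the difference is 1.96 × √(0.9 × 0.1 × (1/304 + 1/152)) = 5.8 points, against a shift of 1.0 point. The GMT is therefore much more exposed than seroprotection.

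**The case against.** The strongest reply is that the bias is conditional. A participant must ask for the group, plan endemic travel, take a licensed dose and then give another sample. The documents do not say how many will. This stands. A reader might infer that vYF persistence is certain to be inflated, and in that arm alone. The text supports only that it can be, with an asymmetric prompt; a Stamaril recipient could also be revaccinated.

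A reader might also infer that the bias grows every year on every parameter. It can accumulate for GMT and seroprotection. It does not for GMTR and seroconversion, which are measured against the previous visit.

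The SafAS rule might be read as proof that the sponsor handled the problem for safety and overlooked it for titres. Its wording, on safety data recorded for a vaccine outside the protocol design, does not clearly remove all later safety data. The contrast is only suggestive.

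The analysis is descriptive (SAP 5.1.2.1), and the primary comparison is made at D29. That too stands, and limits the severity. Using all samples could be defended as a deliberate as-observed estimand, but neither document presents it as one.

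Finally, exclusion is not free of bias. Investigators also receive titres, so low titres could prompt revaccination. Dropping later samples would then remove low responders and overstate vYF persistence. This is a good argument for showing both analyses, not for having no rule.

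**Conclusion.** The gap is real. The plan creates an arm-specific prompt to take a licensed YF vaccine, records that vaccine, and then does not use the record when summarising persistence. vYF estimates can be inflated, mainly from Y2.

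The size cannot be known from the documents. It is zero without revaccination. Under assumed uptake of 2–20% with a persisting 4- to 16-fold rise, it is about 3–74% on the vYF GMT. Seroprotection rises by up to about 2 points at a true rate of 90%, and by no more than 0.4 points at 98%. These figures take revaccination to be confined to the vYF arm and unrelated to prior titre; waning of the boost or non-response to it would make them smaller.

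A reader might go further and doubt the non-inferiority result. The documents do not support that: the D29 sample is drawn before the listings are due to be released. This should be fixed for the persistence objective and does not threaten the primary conclusion.

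**What to change.** - **Main analysis.** In SAP 5.1.2.2 and 5.3.1, state that YF titres drawn after any recorded non-study YF vaccination are excluded, in both arms, from the main Y1–Y5 GMT, GMTR, seroconversion and seroprotection summaries. For the year-on-year parameters, drop any pair in which a sample follows such a vaccination.
- **As-observed analysis.** Show the all-samples FAS result alongside, because revaccination prompted by low titres would make the exclusion informative.
- **Description.** Tabulate revaccination by arm and visit, with the last titre before it, so that readers can judge how informative the exclusion is.
- **Timing.** Add the rule before the yearly analyses are run; added after unblinded yearly results, it would look data-driven.

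The cost is SAP wording, one flag derived from data already collected, and a slightly smaller n at late visits, mainly in the vYF arm. Nothing here bears on the travel advice to participants, only on how the resulting samples are analysed.
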